#### **5.1.1.2 Immunogenicity**

Administration of therapeutic proteins may lead to the formation of ADAs. The development of ADAs may have an impact on exposure and/or efficacy and can lead to hypersensitivity reactions, including immune complex-mediated responses.

Serum samples will be collected at protocol-defined intervals to monitor for the development of ADAs. Patients who have clinical sequelae that are considered potentially related to an ADA response may also be asked to return for additional follow-up testing.

ADAs to RO7297089 were observed in cynomolgus monkeys in the toxicity studies, and while an effect on the pharmacokinetics was noted in cynomolgus monkeys, this does not always translate to an effect in humans. There were no adverse findings related to ADA.

As seen with other therapeutic monoclonal antibodies, RO7297089 can form protein aggregates. Non-covalent multimers (predominantly dimers) have been characterized during manufacturing. The impact of non-covalent multimers or aggregates of RO7297089 is not known; however, there could be an increased potential for immunogenicity (Rosenberg 2006).

Patients will be monitored as described above after infusion for any IRR or hypersensitivity reactions, and at regular intervals for the development of ADAs. Any clinical signs and symptoms suggestive of a hypersensitivity reaction, in particular immune complex-mediated reaction possibly due to ADA formation, will be carefully investigated.

Please refer to the RO7297089 Investigator's Brochure for additional details.

#### **5.1.1.3 Infection**

Due to its anticipated mode of action resulting in plasma-cell depletion and, potentially, NK-cell depletion, RO7297089 may be associated with hypogammaglobulinemia and an increased risk of infections. Serum Ig levels will be monitored in this study according to the schedule outlined in [Appendix 1](#). Administration of IVIg should be considered for patients with hypogammaglobulinemia who are considered to be at increased risk for infection.

In the repeat-dose toxicity study in cynomolgus monkeys, decrease in plasma cells and hypogammaglobulinemia was not seen; however, decreases in serum IgM and mRNA expression levels of plasma cell markers were noted in all monkeys at all dose levels. This was considered a PD effect of the drug.

RO7297089 should not be administered in the presence of active severe infections. Investigators should exercise caution when considering the use of RO7297089 in patients with history of recurring or chronic infections or with underlying conditions that may predispose patients to infections. Signs and symptoms of infection should result in prompt evaluation and appropriate samples for bacteriological investigation prior to starting antibiotic or other treatment.

Hepatitis B reactivation has been reported with B cell-directed therapies. While B cells are not expected to be effected by RO7297089, patients with a history of chronic hepatitis B infection or positive test results for active or chronic HBV infection (defined by HBsAg and/or positive total HBcAb and positive HBV PCR), or patients with HCV infection as assessed by PCR, will be excluded from this trial as a precaution (see Section [4.1.2](#)). Patients with positive HBV serology but undetectable HBV PCR will be allowed to enroll and may receive HBV prophylaxis at the investigator's discretion.

Patients with known or suspected chronic active Epstein-Barr virus infection will be excluded from this trial due to the risk of secondary macrophage activation syndrome (MAS) or hemophagocytic lymphohistiocytosis (HLH) (see Section [4.1.2](#)).

#### **5.1.1.4 Blood Pressure Decrease**

In the 4-week IV repeat-dose GLP toxicity study in cynomolgus monkeys, a core battery of safety pharmacology endpoints were assessed, including external multi-lead electrocardiogram (ECG) and non-invasive blood pressure measurements via tail cuff

measurements 24 hours after completion of infusion on Days 9 and 30 of the study. All ECG parameters were normal, as were measurements of pulse rate. The only findings were minimally decreased systolic, diastolic, and mean arterial pressures (19%, 27%, and 20%, respectively) compared to control animals. These changes were noted on Day 30 in the cohort receiving 50 mg/kg of RO7297089 approximately 24 hours post administration of the fifth scheduled dose. These changes were considered non-adverse in the cynomolgus monkey based on the known variance using tail cuff measurements as a measure of blood pressure, lack of correlating cardiovascular parameters, and lack of clinical correlation in the monkeys; however, a relationship to RO7297089 was unable to be ruled out and, as such, a minimal decrease in blood pressure is considered a potential risk when dosing RO7297089 in humans.

Blood pressure will be monitored during this study according to Section 4.5.5 and the schedule of activities (Appendix 1). This will include measurements of blood pressure during infusion of RO7297089 as well as measurements of blood pressure during post-infusion observation periods. In addition, patients will be educated on the potential for blood pressure decreases and will be instructed to inform their study physicians of any changes in blood pressure or clinical signs and symptoms that could indicate blood pressure decrease such as dizziness, lightheadedness, or syncope.

#### **5.1.1.5 Tumor Lysis Syndrome**

TLS is a known PD effect of anti-tumor therapy in hematologic malignancies including MM (Fuente et al. 2004; Sezer et al. 2006). TLS has been reported with some therapies for MM (Velcade USPI and SmPC; Kyprolis® [carfilzomib] USPI and SmPC). The inherent risk of TLS is dependent on the malignancy being treated and individual patient characteristics (Coiffier et al. 2008). There is a theoretical risk of TLS if treatment with RO7297089 results in the rapid destruction of a large number of tumor cells.

Due to the potential risk of TLS following RO7297089 administration, patients must have a CrCl  $\geq$  30 mL/min to participate in this trial (see Section 4.1.1). Prior to dosing during Cycle 1 of RO7297089, the patient's serum chemistry and hematology laboratory samples should be obtained and reviewed and prophylactic measures initiated according to the guidelines described below. Laboratory results should be reviewed and electrolyte values should not demonstrate any clinically significant abnormalities prior to the infusion of RO7297089 in Cycle 1 and beyond, otherwise the patient should receive additional prophylactic treatment and hydration prior to the initiation of dosing. Laboratory abnormalities suggestive of TLS should prompt immediate action by the treating clinicians, and TLS should be treated aggressively per institutional practice. Access to nephrologist and acute dialysis services must be available in the event of clinically significant TLS.

Patients with elevated uric acid levels prior to RO7297089 treatment or who are considered to be at high risk for TLS as defined in Appendix 14 should receive

prophylaxis for TLS prior to each RO7297089 infusion during Cycle 1 as per institutional guidelines.

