#### 4.1.1 **Inclusion Criteria**

Patients must meet the following criteria for study entry:

- Signed Informed Consent Form
- Age  $\geq 18$  years at time of signing Informed Consent Form
- Ability to comply with the study protocol, in the investigator's judgment
- Eastern Cooperative Oncology Group (ECOG) Performance Status of 0 or 1  
ECOG Performance Status of 2 due to MM may be eligible after discussion with the Medical Monitor.
- Life expectancy of at least 12 weeks
- Patients must have R/R MM for which no established therapy for MM is appropriate and available or be intolerant to those established therapies
- Agreement to provide bone marrow biopsy and aspirate samples as detailed in [Appendix 1](#)
- Adverse events from prior anti-cancer therapy resolved to Grade  $\leq 1$ , with the following exceptions:
  - Any grade alopecia
  - Peripheral sensory or motor neuropathy that has resolved to Grade  $\leq 2$
- Measurable disease, defined as at least one of the following:
  - Serum monoclonal protein (M-protein)  $\geq 0.5$  g/dL ( $\geq 5$  g/L)
  - Urine M-protein  $\geq 200$  mg/24 hr
  - Serum free light chain (SFLC) assay: Involved SFLC  $\geq 10$  mg/dL ( $\geq 100$  mg/L) and an abnormal SFLC ratio ( $<0.26$  or  $>1.65$ )
- Laboratory values as follows:
  - Hepatic function:
    - AST and ALT  $\leq 3 \times$  ULN
    - Total bilirubin  $\leq 1.5 \times$  ULN  
Patients with a documented history of Gilbert syndrome and in whom total bilirubin elevations are accompanied by elevated indirect bilirubin are eligible.
  - Hematologic function:
    - Platelet count  $\geq 50,000/\text{mm}^3$  without transfusion within 7 days of assessment
    - ANC  $\geq 1000/\text{mm}^3$
    - Total hemoglobin  $\geq 8$  g/dL without transfusion within 14 days of assessment

Patients who do not meet criteria for hematologic function because of MM related cytopenias (e.g., due to extensive marrow involvement by MM) may be enrolled into the study after discussion with the Medical Monitor.

- Creatinine clearance (CrCl)  $\geq 30$  mL/min (either calculated using a modified Cockcroft-Gault calculation or per 24-hour urine collection; inulin or radionuclide-based methods may be used after discussion with Medical Monitor)
- Serum calcium (corrected for albumin) level  $\leq 11.5$  mg/dL (2.9 mmol/L)

Treatment of hypercalcemia is allowed and patient may enroll if hypercalcemia returns to normal with standard treatment.

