#### **4.5.7 Laboratory, Biomarker, and Other Biological Samples**

Samples for the following laboratory tests will be sent to the study site's local laboratory for analysis:

- Hematology: WBC count, RBC count, hemoglobin, hematocrit, platelet count, and differential count (neutrophils, eosinophils, basophils, monocytes, lymphocytes, other cells [if present])
- Chemistry panel (serum or plasma): bicarbonate or total carbon dioxide (if considered standard of care for the region), sodium, potassium, chloride, glucose, BUN or urea, creatinine, total protein, albumin, phosphate, calcium, LDH, total and direct bilirubin, ALP, ALT, and AST
- Coagulation: INR, aPTT, and PT (optional)
- HIV serology: HIV-1/2 antibody
- HBV serology: hepatitis B surface antigen (HBsAg), total hepatitis B core antibody (HBcAb), and (if HBsAg test is negative and total HBcAb test is positive) HBV DNA  
If a patient has a negative HBsAg test and a positive total HBcAb test during screening, an HBV DNA test must also be performed to determine if the patient has an HBV infection.
- HCV serology: HCV antibody and (if HCV antibody test is positive) HCV RNA  
If a patient has a positive HCV antibody test during screening, an HCV RNA test must also be performed to determine if the patient has an HCV infection.
- Quantitative immunoglobulins: IgA, IgG, and IgM
- Pregnancy test  
All women of childbearing potential will have a serum pregnancy test within 7 days prior to initiation of study drug. Urine pregnancy tests will be performed on the first day of odd-numbered cycles. If a urine pregnancy test is positive, patient dosing will be postponed until the result is confirmed by a serum pregnancy test. Patients who become pregnant while on study must permanently discontinue study treatment as outlined in Section 4.6.1.
- Standard-of-care assessments of bone marrow biopsies and aspirate for local clinical pathology assessment, which will include, but are not limited to, cytogenetic analysis by fluorescence in situ hybridization (FISH; including markers such as 1q gain, del17, t(11:14), t(4;14), t(14; 16))  
The results of these studies should be sent to the Sponsor when available (results should be redacted of patient identifiers other than protocol-assigned patient number).
- Serum  $\beta$ -2 microglobulin

Samples for the following laboratory tests will be sent to one of several central laboratories for analysis:

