- l Liver function tests include total and direct bilirubin, total protein, albumin, ALT, AST, ALP.
- m Chemistry panel includes sodium, potassium, chloride, bicarbonate or total carbon dioxide (if considered standard of care for the region), glucose, BUN or urea, creatinine, calcium, phosphorous, LDH.
- n All women of childbearing potential must have a negative serum pregnancy test result within 7 days prior to initiation of study drug. Thereafter, perform a urine pregnancy test on the first day of odd-numbered cycles. If a urine pregnancy test result is positive, patient dosing will be postponed until the result is confirmed by a serum pregnancy test. Patients who become pregnant while on study must permanently discontinue study treatment as outlined in Section 4.6.1.
- o Central testing is required for these assessments.
- p See Section 4.5.7 and specific instructions and description of supplies in the laboratory manual regarding bone marrow sample harvesting. Unsuccessful attempts at marrow aspiration will not be considered a protocol violation.
- q The screening bone marrow biopsy and aspirate may be performed after all other screening tests have been completed and after the Medical Monitor has confirmed that the patient is eligible for the trial. Patients who are re-screened after an initial screen failure (see Section 3.1) do not need to undergo a repeat bone marrow biopsy and aspirate if these assessments were completed during the initial screening period.
- r For Cycles  $\geq 2$ , study drug infusions should occur on Day 1 and Day 8 of each 14-day cycle but may be given up to  $\pm 2$  days from the scheduled date (with a minimum of 5 days between doses) for logistic/scheduling reasons. All timepoints listed are relative to end of infusion unless otherwise noted.

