## **Appendix 14**

### **Criteria for Identifying Multiple Myeloma Patients at High Risk for Tumor Lysis Syndrome**

Reference: Minasyan and Henrici 2015.

Patients meeting any of the following criteria will be considered at high risk for tumor lysis syndrome (TLS):

- Prior history of TLS caused by previous multiple myeloma therapy
- Pre-existing renal insufficiency (serum creatinine  $> 1.5$  mg/dL, or CrCl  $< 60$  mL/min)
- High tumor burden, defined as increased serum LDH ( $> 2 \times$  ULN), increased beta-2 microglobulin ( $\geq 5.5$  mg/dL), hypercalcemia (serum Ca  $> 12$  mg/dL), or per investigator's clinical judgment (e.g., based on the magnitude of diffuse bone marrow disease and multiple lytic lesions)

## Appendix 15

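### Elevated uric acid is a stand-alone trigger for tumor lysis prophylaxis, but no scheduled laboratory panel measures it

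*Combined protocol and SAP*

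**What the plan says.** Section 5.1.1.5 ties TLS prevention to laboratory work done before dosing in Cycle 1: "the patient's serum chemistry and hematology laboratory samples should be obtained and reviewed and prophylactic measures initiated according to the guidelines described below". It then names who is to be treated: "Patients with elevated uric acid levels prior to RO7297089 treatment or who are considered to be at high risk for TLS" as set out in Appendix 14. These patients should receive "prophylaxis for TLS prior to each RO7297089 infusion during Cycle 1 as per institutional guidelines". The section gives no threshold for an elevated uric acid.

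The chemistry panel is itemised in two places that govern the treatment period. Section 4.5.7 ends its list with "creatinine, total protein, albumin, phosphate, calcium, LDH, total and direct bilirubin, ALP, ALT, and AST". Appendix 1 footnote m ends with "glucose, BUN or urea, creatinine, calcium, phosphorous, LDH". Appendix 2 footnote d repeats the Appendix 1 list for post-treatment follow-up. None of them includes uric acid.

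**The concern.** The plan states a safety trigger and then schedules no test that would supply its value. This is not a matter left to judgment: the trigger is explicit, and the same section points to the pre-dose chemistry sample as the basis for starting prophylaxis.

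At stake is whether a safeguard is applied evenly. TLS is listed among the anticipated risks of this first-in-human trial (Section 1.3) and is an adverse event of special interest (Section 5.2.3). If one site adds uric acid to its local panel and another does not, two similar patients can be handled differently in Cycle 1. The trial database would not show why, because the value is not a scheduled item.

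**Working it through.** No sample size or error rate is involved and the plan states no figure to reproduce, so the check compares passages.

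**1. Is uric acid a separate trigger?** Yes. Section 5.1.1.5 joins elevated uric acid and Appendix 14 high risk as alternatives, and Appendix 14 does not list uric acid. Meeting or failing Appendix 14 therefore says nothing about the uric acid trigger.

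**2. Is it measured anywhere on schedule?**
- Chemistry lists (Section 4.5.7; Appendix 1 footnote m; Appendix 2 footnote d): uric acid in 0 of 3, calcium in 3 of 3.
- Hematology list (footnote k), liver list (footnote l) and the remaining Appendix 1 rows: absent.
- Section 5.1.1.5 contains the only mention of uric acid in the document.

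The chemistry lists read as complete. Other entries in Section 4.5.7, such as the cytokine and flow cytometry samples, are expressly open-ended; the chemistry entry is not.

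**3. Are the other laboratory markers in the screen measured?**

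| Laboratory marker | Where it acts as a trigger | Scheduled source |
|---|---|---|
| Creatinine or creatinine clearance | Appendix 14 | Chemistry panel |
| LDH | Appendix 14 | Chemistry panel |
| Beta-2 microglobulin | Appendix 14 | Own row in Appendix 1, at screening |
| Calcium | Appendix 14 | Chemistry panel |
| Uric acid | Section 5.1.1.5 | None |

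Four of five are scheduled and one is not. That pattern suggests an omission rather than a policy.

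**4. At which draws would the value be needed?** Prophylaxis is decided before each Cycle 1 infusion. Arms A and C have two such infusions (Days 1 and 8). Arm B has three (Days 1, 2 and 8). Appendix 1 footnote b has local samples drawn within the 24 hours before infusion in Cycle 1 and reviewed before dosing. Adding the screening draw:
- Arms A and C: 1 + 2 = 3 chemistry draws that could inform the decision.
- Arm B: 1 + 3 = 4 such draws.

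Uric acid is scheduled at none of them, although the blood is taken at all of them.

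**The case against.** **Sites may measure uric acid anyway.** This stands in part. Nothing prevents local testing, so the trigger is unsupported by the schedule rather than impossible to use. But the deferral to institutional guidelines in Section 5.1.1.5 concerns the prophylaxis, and no text tells a site to obtain the value.

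**The rest of the screen still works.** This stands. Any one Appendix 14 criterion is enough, and prior TLS, renal function, LDH, beta-2 microglobulin, calcium and investigator judgment all remain available. Section 5.1.1.5 also calls for extra prophylaxis and hydration when pre-infusion electrolytes are abnormal to a clinically significant degree. It describes the TLS risk as theoretical.

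**A reader might go further and infer that the Appendix 14 calcium item cannot operate either.** That item is "hypercalcemia (serum Ca $> 12$ mg/dL), or per investigator's clinical judgment", while Section 4.1.1 caps "Serum calcium (corrected for albumin) level" at 11.5 mg/dL, and 12 − 11.5 = 0.5 mg/dL. The documents do not support the inference, for four reasons:
- Appendix 14 does not tie its calcium value to screening. Screening chemistry may be up to 14 days old (Section 4.5), and calcium is redrawn before each Cycle 1 infusion. Nothing stops a later value from exceeding 12 mg/dL.
- Section 4.1.1 lets patients with corrected hypercalcemia enroll, so an earlier high value is possible in an enrolled patient.
- The entry limit is albumin-corrected and the Appendix 14 limit is not stated to be, so the 0.5 mg/dL difference may compare two different measures. The documents give no correction formula. Assuming corrected = total + k × (reference albumin − albumin), total calcium above 12 with corrected calcium at or below 11.5 requires albumin above reference + 0.5/k. With k = 0.8 to 1.0 and a reference of 4.0 to 4.4 g/dL, that is about 4.5 (4.0 + 0.5/1.0) to 5.0 g/dL (4.4 + 0.5/0.8 = 5.025). The window is narrow but not empty.
- The electrolyte provision in Section 5.1.1.5 acts on a clinically significant calcium abnormality whatever Appendix 14 says.

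What remains on calcium is a lack of clarity: Appendix 14 does not say whether its value is total or corrected, or at which timepoint it applies.

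**Conclusion.** The point holds for uric acid. Section 5.1.1.5 uses it as an independent trigger before each Cycle 1 infusion, and the schedule provides it at 0 of the 3 relevant draws in Arms A and C and 0 of the 4 in Arm B. As written, the trigger works only where a site tests on its own initiative, and practice may vary across the approximately 12 sites.

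The number of patients affected is unknown. It is limited to those among the 60–80 planned whose only risk marker is uric acid, and the documents give no frequency. The conclusion assumes that the itemised chemistry lists are complete as printed.

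A reader might also infer that patients with high uric acid will enter Cycle 1 unrecognised, or that TLS will be under-counted as an event of special interest. Neither is shown. Other triggers or local testing may identify the same patients. Section 5.2.3 lists TLS as Grade 3 or higher by definition, and no passage makes uric acid part of that definition. Potassium, phosphate, calcium, creatinine and LDH are all collected.

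**What to change.** Reconcile Section 5.1.1.5 with Section 4.5.7 and Appendix 1 footnote m by adding uric acid to the chemistry panel at screening and at the Cycle 1 pre-infusion chemistry timepoints (Days 1 and 8, and Day 2 in Arm B). The samples are already drawn, so no extra visit or procedure is needed. The cost is one additional routine local analyte and a wording change in the panel definitions.

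In the same amendment the sponsor could state whether the Appendix 14 calcium value is total or albumin-corrected and at which timepoint it applies, so that it can be read alongside the corrected-calcium limit in Section 4.1.1. The calcium item itself need not be changed or removed on the grounds considered here. No cutoff is proposed for uric acid or calcium; that is for the sponsor's clinicians.

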#### **5.1.1.6 Lymphopenia**

Given the mode of action of RO7297089 mediating destruction of BCMA-expressing plasma cells via engagement of CD16A expressed on NK cells in a manner similar to ADCC, reduction in lymphocyte counts is a potential risk.

In patients with R/R Hodgkin Lymphoma treated with single-agent AFM13, a transient dose-dependent decrease of circulating NK cells was observed. This was felt to be due to margination, but could possibly have been an effect of the drug given the mechanism of action (Rothe et al. 2015).

Patients receiving RO7297089 will be monitored for decreases in lymphocytes as described in [Appendix 1](#). In addition, Grade  $\geq 3$  lymphopenia that also represents  $\geq 50\%$  decrease from baseline (regardless of whether the event otherwise meets criteria for reporting of an abnormal laboratory value as an adverse event) will be considered an adverse event of special interest for this study. Patients with lymphopenia may be considered for antiviral and PCP prophylaxis as per institutional standard.

### **5.1.2 Management of Patients Who Experience Adverse Events**

#### **5.1.2.1 Dose Modifications and Interruptions**

All considerations of dose and schedule modifications should be discussed with the Medical Monitor. The following guidelines regarding dose and schedule modifications should be followed:

- In general, patients receiving RO7297089 who experience a Grade 4 non-hematologic adverse event that is not considered by the investigator to be attributable to another clearly identifiable cause should permanently discontinue all study treatment. However, for patients with Grade 4 adverse events of asymptomatic laboratory changes, study treatment may be resumed upon resolution to Grade  $\leq 1$  or baseline with approval of the Medical Monitor.
- For patients who experience IRRs with the first dose of RO7297089, or are at increased risk of recurrent IRRs with subsequent doses, the infusion rate may be slowed by 50% (Section [5.1.2.2](#)). Modifications to infusion rate in these circumstances should be discussed with the Medical Monitor.
- In general, patients who experience either an adverse event that meets the definition of a DLT or other Grade 3 adverse event that is not considered by the investigator to be attributable to another clearly identifiable cause (e.g., documented disease progression, concomitant medication, or pre-existing medical condition) will be allowed to delay dosing for up to 2 weeks (or longer if approved by the Medical Monitor) in order to recover from the toxicity. Patients may continue to receive additional infusions of RO7297089, provided that the toxicity has resolved to Grade  $\leq 1$  (or for laboratory abnormalities, return to  $\geq 75\%$  of the baseline value), within 2 weeks.

- A reduced dose for subsequent infusions of RO7297089 should be considered and discussed with the Medical Monitor. Decisions on continued treatment following a DLT or other study treatment–related Grade 3 toxicity should be made following a careful assessment and discussion of risk versus benefit with the patient by the investigator and approval of the Medical Monitor, including in the following scenarios:
  - Patients with Grade 3 or 4 event of anemia if manageable by red blood cell transfusions as per institutional practice may continue without dose reduction with approval of the Medical Monitor.
  - Patients with Grade 3 or 4 events of thrombocytopenia or neutropenia if manageable by transfusions (platelets) or granulocyte colony-stimulating factor (GCSF) as per institutional practice may continue without dose reduction with approval of the Medical Monitor.
- Any patient in whom similar toxicity recurs at a reduced dose should be discontinued from further RO7297089 treatment.
- Patients who do not fulfill the criteria for dosing after the additional 2 weeks have elapsed will be discontinued from study treatment (unless a longer dose delay was approved by the Medical Monitor) and be followed for safety outcomes as described in Section 5.3.1. Exceptions to this on the basis of ongoing clinical benefit may be allowed following investigator assessment of risk versus benefit with approval of the Medical Monitor. In addition, delay of therapy because of toxicities not attributed to study drug may not require discontinuation and will be discussed with the Medical Monitor.

The dose of RO7297089 can be reduced up to two times for management of drug-related toxicities. If further dose reduction is indicated after two dose reductions, the patient must discontinue RO7297089. After dose reduction due to drug-related toxicity, the dose of RO7297089 may not be re-escalated.

Patients who discontinue study treatment for reasons other than progressive disease should continue to be followed according to the schedule in [Appendix 3](#).

